The Nephrotic Syndrome Study Network (NEPTUNE) has been created and charged with the purpose of accomplishing the specified study goals. NEPTUNE is comprised of individuals with outstanding dedication and multi-disciplinary investigative expertise. NEPTUNE came into being in large part due to the unflinching support, and significant commitment from the NephCure Kidney International, previously known as The NephCure Foundation, which is a lay research non-profit foundation devoted to understanding and improving the treatment of FSGS. NEPTUNE will operate in full with NephCure. The Halpin Foundation is also a lay research foundation that is supportive, committed and fully engaged with NEPTUNE. NEPTUNE was initially funded primarily through a 5-year grant award (U54 DK083912) from the NIDDK and ORD (\$6.25 million) with additional funding from NephCure (\$2.0 million) and the Regents of the University of Michigan (\$2.0 million). It has received a subsequent 5 year grant award (U52 DK083912-06) from the NIDDK (\$5.81 millions) and the Regents of The University of Michigan (\$4.2 million).

1.C. Specific Aims – Cohort A (Biopsy Group)

Participants presenting with Nephrotic Syndrome will be initially enrolled into two main concurrent cohort studies, namely the FSGS/MCD Cohort Study and the MN Cohort Study. The specific aims and research hypotheses of each of the main cohort studies and the combined cohort are outlined below.

1.C.1. Aims Related to FSGS and MCD

Specific Aim 1: To determine the rates and predictors of clinical remission of FSGS/MCD.

Hypothesis 1: After accounting for the types, duration, and frequency of immunomodulating therapy, the probability of remission of FSGS/MCD defined as change in urinary protein excretion and/or renal function

will be predicted by baseline demographic, clinical, genetic and histopathological characteristics at the time of presentation.

Specific Aim 2: To identify gene expression profiles from renal biopsies of participants with FSGS/MCD that can be used to classify participants into distinct molecular subgroups.

Hypothesis 2: Genome-wide molecular profiles obtained from renal biopsy tissue at the time of diagnosis of FSGS/MCD will independently predict the rate of remission of FSGS/MCD defined as change in urinary protein excretion and change in renal function.

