Other measures, including screen failure for consented individuals determined to have exclusion criteria present post-enrollment, have been taken to compensate for over-enrolling in the OG group. The OG group will not be further followed, but samples and data obtained will remain available for comparative analyses.

3.F.3. Special Considerations for the Analysis of Molecular Biomarkers

[figure not shown]
The analysis of molecular biomarkers aims to identify promising genetic signatures used in the building of a prediction model for clinical outcomes. To screen the large number of potential predictors without losing analytical power, we would proceed in a hypothesis generating manner. Regression analysis of the clinical endpoint on biomarkers allows us to obtain P-values in the testing of their association, and a threshold value of false discovery rate would be set to determine a pool of potentially important biomarkers. These selected biomarkers will then be analyzed and grouped according to the relevance of their biological functions available in various databases. For example, biomarkers in a common transcriptional network may form a molecular signature panel. Such various panels can be further tested for the association with the clinical endpoint via the method of ridge regression. Ridge regression enables us to bypass the analytic difficulty due to highly correlated biomarkers in the model and hence obtain robust results.

3.F.4. Prediction Model Combining Molecular Biomarkers and Auxiliary Variables

The primary objective of the data analysis is to build a predictive model that uses both molecular biomarkers and auxiliary predictors to classify patients into one of two clinical states of the primary endpoint, Complete Remission/Partial Remission (CR/PR) and No Remission/Relapse (NR/R). The second endpoint is the presence or absence of the loss of renal function. In addition to 20,000 molecular markers, there are 74 auxiliary predictors collected from both cohort studies, including 38 histopathology variables, 15 laboratory variables, 15 clinical and demographic information variables, and 6 treatment variables.

Given the large number of predictors, we take a three-stage data analysis strategy consisting of variable screening, model building, and model validation. Figure 1 shows a schematic flow of steps for the model building.

Figure 1: Schematic illustration of analytic steps taken to model building.

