The first stage of analysis is a variable screening analysis, in which we perform univariate analysis. The aim of this study is to evaluate basic distributional characteristics of each predictor and pairwise correlation between the response and each predictor, as well as that between each pair of predictors. In this analysis, we also examine if transformations on some predictors are needed and if high-order predictors such as interactions and polynomial predictors are potentially useful predictors.

At the second stage of analysis, we build a predictive model for the clinical endpoint. First, we perform univariate logistic regression of the clinical endpoint on each of the predictors to detect promising predictors. To deal with the multiplicity in the test, we control a common significance level α_m on molecular markers and α_c on auxiliary predictors. At different levels of α_m and α_c , we obtain several sets of molecular and auxiliary predictors. For example, we may control α_m at 10^{-8} and α_c at 10^{-4} according to the Bonferroni's conservative type I error control. Using a set of the selected predictors, we invoke ridge logistic regression to build a predictive model, which essentially provides a linear classifier to determine the membership of a patient with a clinical class.

At the final stage of model building, we use the ROC curve method to select the final model from a small pool of candidate predictive models. To do this, we split the sample into the training set and the test

set at $(2/3n):(1/3n)$ (96-98) randomly with multiple rounds, say 100. For the sample size 200, the split is 135:65, and for the sample size of 250, the split is 170:80. At each round, we use the training set to build a predictive model and the test set to evaluate its performance of prediction by the AUC, acronym for the area under the receiver operating characteristic (ROC) curve. We use the averaged AUC to determine the final predictor model with the best averaged prediction power.

3.F.5. Sample Size and Power Considerations

3.F.5.a. Overview

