The primary aim of this study is to build up the prediction model, so our sample size and power calculation should be based on this goal. Following Dobbin and Simon (96), we adopt the expected probability of correct classification (PCC) as the measure of predictive power, which is approximately equal to the AUC, acronym for the area under the receiver operating characteristic (ROC) curve. This study focuses on two rare diseases: FSGS/MCD and MN, so we use PCC to evaluate the sample size of these two diseases, respectively.

3.F.5.b. Sample Size and Power Related to the FSGS/MCD Cohort Study

PCC is the probability of correct classification obtained on an infinite sample size and should be the gold standard of the best power. FSGS and MCD are rare diseases; it is unrealistic to find very large sample sizes to approximate the result under an infinite sample size. However, we will be able to find the PCC under realistic sample sizes, and we use PCC* to denote it. PCC* is the expected probability of correct classification with the optimal linear classifier constructed from the true molecular markers and auxiliary predictors. The results given in Table 6 are based on a simplified analysis with conservative assumptions. We screen 20,000 genes (probes) and 75 auxiliary predictors, in which there are r_m true gene expression markers and r_c true auxiliary predictors for the clinical endpoint. Ratio δ_m/σ_m is the average effect size of a single molecular marker, and the relative effect size of the auxiliary predictor to the molecular marker is 0.5. Also, ρ is the correlation between molecular markers and auxiliary predictors, and $\rho=0$ is assumed in Table 7 (3.N-2 below).

Table 7. Probability of Correct Classification

$r_m = 5, r_c = 10$				
δ_m/σ_m	PCC*	PCC(n=100)	PCC(n=150)	PCC(n=200)
0.2	0.788	0.638	0.667	0.687
0.4	0.941	0.876	0.892	0.896
$r_m = 50, r_c = 10$				
δ_m/σ_m	PCC*	PCC(n=100)	PCC(n=150)	PCC(n=200)
0.2	0.941	0.638	0.695	0.753
0.4	0.999	0.987	0.995	0.996
$r_m = 100, r_c = 10$				
δ_m/σ_m	PCC*	PCC(n=100)	PCC(n=150)	PCC(n=200)
0.2	0.982	0.672	0.766	0.837
0.4	0.99999	0.9994	0.99990	0.99994

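### Section 3.F.4 labels example screening levels of 10^-8 and 10^-4 as Bonferroni; they are about 250 and 7 times stricter than Bonferroni at 0.05, and they are not reconciled with the false discovery rate rule in 3.F.3

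*Protocol*

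**What the plan says.** Section 3.F.3 describes the marker screen as hypothesis generating and meant to preserve power. Each biomarker is tested by regression on the clinical endpoint, and "a threshold value of false discovery rate would be set to determine a pool of potentially important biomarkers". No FDR value is given.

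Section 3.F.4 gives the counts: "In addition to 20,000 molecular markers, there are 74 auxiliary predictors collected from both cohort studies". In its second stage, "we perform univariate logistic regression of the clinical endpoint on each of the predictors to detect promising predictors". Markers are held to a common level α_m and auxiliary predictors to a common level α_c. It continues: "At different levels of α_m and α_c , we obtain several sets of molecular and auxiliary predictors". It then gives, as an example that may be used, 10^-8 for α_m and 10^-4 for α_c, "according to the Bonferroni's conservative type I error control". Selected predictors go into a ridge logistic model. The final model is chosen by AUC averaged over repeated splits (135:65 for n=200, 170:80 for n=250).

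Table 7 (section 3.F.5.b) gives the probability of correct classification (PCC) for 5, 50 or 100 true markers of effect 0.2 or 0.4, with 10 true auxiliary predictors at half the marker effect. It does not state its screening level. Its text has a slightly different count: "We screen 20,000 genes (probes) and 75 auxiliary predictors".

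Hypothesis 2 (section 1.C.1) says that molecular profiles "will independently predict the rate of remission of FSGS/MCD". Hypothesis 5 (section 1.C.2) says the same for MN.

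**The concern.** The only numerical screening levels in the protocol are attributed to a correction that does not produce them, and a different error rule is named for the same screen one section earlier. An analyst cannot tell which rule applies.

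The choice matters because Table 7 credits the classifier with many weak true markers. Section 3.F.5.c illustrates the MN sample size with 100 markers of effect 0.2 and a PCC rising from 76.6% to 83.7% between n=150 and n=200. A screen that removes nearly all such markers cannot deliver that.

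The histology, laboratory, clinical and treatment variables face the same one-at-a-time screen at α_c. Known prognostic factors could drop out, and a marker in the resulting model would not thereby have been shown to add to them.

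**Working it through.** **1. Trying to reproduce the stated levels.** Bonferroni per-test level = familywise level / number of tests.

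- Markers: 0.05/20,000 = 2.5x10^-6. Stated 10^-8; ratio 250. Implied familywise level 20,000 x 10^-8 = 0.0002.
- Auxiliary predictors: 0.05/74 = 6.8x10^-4 (6.7x10^-4 for 75). Stated 10^-4; ratio 6.8. Implied familywise level 74 x 10^-4 = 0.0074.

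The implied familywise levels differ from each other, so no single one gives both. Familywise levels from 0.001 to 0.10, pooling to 20,074 tests, Sidak, pairwise interactions, marker-by-auxiliary pairs and multiplication by 100 resampling rounds also fail to give the pair. The 0.05 is the two-sided level in the section 1.B synopsis; none is stated for the screen.

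**2. Share of true markers that pass.** Approximate the univariate logistic test by a two-group comparison with 50:50 classes and unit SD:

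P(pass) ≈ P(Z > z − Δ√n/2), with z = 5.731 for 10^-8 and 4.708 for 2.5x10^-6 (two-sided).

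The protocol does not say whether the effect d is the full distance between class means (Δ = d) or half of it (Δ = 2d). Both are shown.

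For d=0.2, n=200, the shift Δ√n/2 is 1.414 (full) or 2.828 (half):
- At 10^-8: P(Z > 4.317) = 0.0008% to P(Z > 2.902) = 0.19%.
- At 2.5x10^-6: P(Z > 3.294) = 0.05% to P(Z > 1.880) = 3.0%.

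| d | n | pass 10^-8 (full to half) | pass 2.5x10^-6 (full to half) |
|---|---|---|---|
| 0.2 | 135 | 0.0002% to 0.03% | 0.02% to 0.86% |
| 0.2 | 200 | 0.0008% to 0.19% | 0.05% to 3.0% |
| 0.2 | 250 | 0.002% to 0.51% | 0.09% to 6.1% |
| 0.4 | 135 | 0.03% to 14% | 0.86% to 48% |
| 0.4 | 200 | 0.19% to 47% | 3.0% to 83% |
| 0.4 | 250 | 0.51% to 72% | 6.1% to 95% |

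With 100 true markers of effect 0.2 at n=200, even the half-distance reading expects 0.19 to pass 10^-8. The chance that none passes is (1 − 0.00185)^100 = 83%.

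**3. Effect on Table 7.** Take PCC = Φ(sum of selected true effects / √(number of features selected)), with independent features, equal weights and the half-distance reading. The 0.2 rows at n=200 are approximated (0.689, 0.763, 0.844 against 0.687, 0.753, 0.837 in the table) only with a screening level optimised for each row (about 10^-3 for 50 to 100 markers) and a relative auxiliary effect of 1.0. With the stated 0.5 the values are 0.561, 0.707 and 0.815.

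With 10^-8 and 10^-4, the 0.837 cell falls to 0.60 (relative effect 1.0) or 0.52 (0.5). At effect 0.4 with 50 to 100 markers, PCC at n=200 stays at 0.97 to 0.999. In the n=100 column it falls to 0.72 to 0.89, against 0.987 and 0.9994 in the table.

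**4. What an FDR rule would keep.** For 100 true markers of effect 0.2, solve 19,900a / (19,900a + 100·P(pass at a)) = 0.10 on the half-distance reading:
- n=135: a ≈ 1.0x10^-5, about 1.8 markers.
- n=200: a ≈ 7x10^-5, about 13.
- n=250: a ≈ 1.5x10^-4, about 26.

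**5. Auxiliary predictors.** For illustration, take a 50/50 factor with odds ratio 2.5 (assumed, not from the protocol), log odds ratio 0.916 and SE ≈ 4/√n.
- n=250: z-mean 0.916/0.253 = 3.62; it passes 10^-4 (z = 3.891) with probability 0.39.
- n=170: z-mean 0.916/0.307 = 2.99; probability 0.18.
- At 6.8x10^-4 the probabilities are 0.59 and 0.34.

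**The case against.** The strongest reply is that the levels are illustrative. The protocol says they may be used, that several levels will be tried, and that averaged test-set AUC picks the model. If 10^-8 selects almost nothing, another candidate set can win. This stands, and it makes the loss conditional. A reader might infer that the plan fixes these levels and so cannot reach Table 7, or that 3.F.3 and 3.F.4 flatly contradict each other. The text supports neither: one section names an FDR rule without a value, and the other gives an optional example.

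Four further points stand:

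- Levels that are too strict still control type I error; the cost is power.
- The shortfall does not cover all of Table 7. The FSGS/MCD worked example (50 markers, effect 0.4, n=200, 99.6%) largely survives on the half-distance reading, which fits the table best.
- The wrong label is not the main cause of the loss. Correct Bonferroni keeps at most about 3 of 100 weak markers at n=200.
- An FDR rule does not restore the 0.2 rows either. With 10% FDR, even ideal weights and all ten auxiliary predictors give a PCC of at most about 0.66 at n=135 and 0.78 at n=200, against 0.837 in the table.

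It is also tempting to say that Hypotheses 2 and 5 become untestable. That goes too far: the ridge model combines both predictor types, section 3.F.1 mentions adjusted hazard rates, and section 3.F.5.e plans Cox models. What remains is that screening clinical factors by p-value weakens the claim of independent prediction from the classifier itself.

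**Conclusion.** The concern holds in limited form. Two points rest on the document's own figures: 10^-8 and 10^-4 are not Bonferroni levels for 20,000 and 74 tests (250 and about 7 times too strict at an assumed 0.05, and matched by no common familywise level), and two error rules for one marker screen are left unreconciled.

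The consequence is conditional. If levels near the example were used, at least 99.8% of true markers of effect 0.2 would be lost at n=200 and 99.4% at n=250, and Table 7's 0.2 rows could not be reached. These figures assume 50:50 classes, a normal approximation and independent features; the range covers both readings of the effect size. On the half-distance reading the effect-0.4 rows with 50 to 100 markers are largely unaffected at n=200; on the full-distance reading only 0.19% of those markers would pass 10^-8.

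This should be corrected, but it does not threaten the validity of the study. The difference between 74 and 75 auxiliary predictors is immaterial here.

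**What to change.** 1. Delete the example in 3.F.4, or correct it to 2.5x10^-6 and 6.8x10^-4 and state the familywise level of 0.05.
2. Use one error rule for the marker screen in 3.F.3 and 3.F.4, for example Benjamini-Hochberg FDR at 10%, applied inside each training set.
3. State the screening level and the effect-size definition behind Table 7. Restate its 0.2 rows for the rule and training size actually used, since 10% FDR at n=135 keeps only about 2% of such markers.
4. Keep a prespecified set of clinical, histology and baseline-treatment predictors in the ridge model without p-value screening.
5. Report test-set AUC for clinical-only and clinical-plus-molecular models on the same splits, to address Hypotheses 2 and 5 directly.
6. Use one count of auxiliary predictors throughout.

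The cost is statistical wording and some recalculation; no data collection changes. A few more false-positive markers and uninformative covariates will enter a penalised model, and the restated PCC figures may be less favourable.

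### Section 3.F.4 screens predictors on the outcome before the train/test split and picks the final model by the AUC from that split, so the AUC is optimistic unless the screen is very strict

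*Protocol*

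**What the plan says.** Section 3.F.4 makes a predictive model for remission the primary objective of the data analysis and announces three stages: screening, model building and validation. The candidate predictors are many: "In addition to 20,000 molecular markers, there are 74 auxiliary predictors collected from both cohort studies".

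- **Stage 1** looks at the correlation of each predictor with the response and considers transformations, interactions and polynomial terms.
- **Stage 2** opens with the outcome again: "First, we perform univariate logistic regression of the clinical endpoint on each of the predictors to detect promising predictors". It then says "At different levels of α_m and α_c , we obtain several sets of molecular and auxiliary predictors". One pair of levels, 10^-8 for markers and 10^-4 for auxiliary predictors, is offered as an example "according to the Bonferroni's conservative type I error control". Ridge logistic regression is fitted to a selected set.
- **Stage 3** brings in the split for the first time: "we use the ROC curve method to select the final model from a small pool of candidate predictive models". The split is 2/3 to 1/3, repeated about 100 times. In each round a model is built on the training set and its AUC taken on the test set. The stage ends: "We use the averaged AUC to determine the final predictor model with the best averaged prediction power".

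Section 3.F.3 describes a different marker screen, in which "a threshold value of false discovery rate would be set to determine a pool of potentially important biomarkers". No false discovery rate level is given.

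**The concern.** A test set gives an honest AUC only if its participants played no part in choosing the predictors. In the order given, the predictor sets exist before the split, and they were formed by testing every predictor against the outcome. A noise marker that passes the screen does so because it happens to separate the classes in this sample, test participants included. It will separate them again in any random third of the same sample.

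Two consequences follow. The averaged AUC overstates performance. And because that AUC chooses among sets made at different alpha levels, it favours the set that admitted the most chance associations. Both affect the stated primary objective, and 3.F.4 describes nothing independent against which the chosen model would be checked.

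**Working it through.** **Inputs from the protocol.** 20,000 markers; 74 auxiliary predictors in 3.F.4 (3.F.5.b has "We screen 20,000 genes (probes) and 75 auxiliary predictors", a difference that does not matter here); target sizes 250 (FSGS/MCD) and 200 (MN) in 3.F.2; marker effect δ/σ = 0.2 and auxiliary effect half of that in 3.F.5.b.

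**The plan's own figures.** The protocol states no AUC, so only the split can be reproduced. 200 × 2/3 = 133.3 against 135 stated; 250 × 2/3 = 166.7 against 170 stated. Both are rounding.

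**Assumptions not in the protocol.** Independent normal predictors, 50% outcome prevalence, ridge penalty 10 on standardised predictors, a score test in place of the logistic Wald test, an empty set scored as AUC 0.5, and every threshold pair except the first in the table below.

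**Step 1: how many null predictors pass.** Expected number = 20,000·α_m + 74·α_c. Chance of at least one = 1 − (1−α_m)^20000 · (1−α_c)^74.

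| α_m / α_c | Expected null predictors | Chance of any |
|---|---|---|
| 10^-8 / 10^-4 (protocol example) | 0.0002 + 0.0074 | 0.8% |
| 2.5×10^-6 / 6.8×10^-4 (5% Bonferroni) | 0.05 + 0.05 | 9.5% |
| 10^-4 / 0.01 | 2.0 + 0.74 | 94% |
| 10^-3 / 0.01 | 20 + 0.74 | about 100% |
| 0.01 / 0.05 | 200 + 3.7 | about 100% |

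**Step 2: averaged AUC with no informative predictor (true value 0.50).** Screening once on everyone and then averaging over 100 splits is compared with re-screening inside each training set (60 replicates at n=200, 40 at n=250).

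| α_m | Screen first, n=200 | Screen first, n=250 | Screen inside, n=200 |
|---|---|---|---|
| 10^-8 | 0.500 | 0.500 | 0.500 |
| 2.5×10^-6 | 0.509 | 0.512 | 0.499 |
| 10^-4 | 0.701 | 0.677 | 0.500 |
| 10^-3 | 0.920 | 0.889 | 0.499 |
| 10^-2 | 1.000 | 0.999 | 0.499 |

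Other implementations at n=200, differing in the form of ridge and the number of splits, gave 0.67 to 0.76 at 10^-4, 0.91 to 0.93 at 10^-3 and 0.99 to 1.00 at 10^-2.

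**Step 3: how much comes from reusing the AUC to select.** With screening inside the training set, the best of the five levels chosen on its own AUC averages 0.52. Selection alone therefore adds about 0.02; the rest is the leak.

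**Step 4: with real but modest signal.** n=200, 50 true markers of effect 0.2 (class means at ±δ), 10 true auxiliary predictors, 40 replicates.

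| α_m | Apparent AUC | AUC in new patients |
|---|---|---|
| 10^-8 | 0.51 | 0.51 |
| 2.5×10^-6 | 0.66 | 0.59 |
| 10^-4 | 0.88 | 0.73 |
| 10^-3 | 0.98 | 0.78 |
| 10^-2 | 1.00 | 0.74 |

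The averaged AUC picks the loosest set, which shows 1.00 but delivers 0.74, although the 10^-3 set delivers 0.78.

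**Step 5: the example thresholds.** 5% Bonferroni gives 0.05/20,000 = 2.5×10^-6 and 0.05/74 = 6.8×10^-4. The example is 250 times stricter for markers (2.5×10^-6 / 10^-8) and about 7 times stricter for auxiliary predictors. With class means at ±δ, the chance that a true marker passes is Φ(effect·√n − z). For effect 0.2, n=200 and α=10^-8 this is Φ(2.83 − 5.73) = 0.2%. If the distance between the class means is only δ, it is practically zero.

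**The case against.** **Screening inside each round may be what is meant.** The protocol never says that screening uses the full sample. Stage 2 presents univariate screening as the first step of building a model, and stage 3 says that a model is built on the training set in each round, so re-screening could be included. Figure 1, which illustrates the steps, was not legible in the text available to me. This reading is possible but less natural. Stage 2 already yields the sets from which stage 3 chooses, and the ridge fit on a selected set is also described as building a model. If screening were redone each round, no fixed pool of sets would remain. Stage 1 would still use the outcome before the split. The point that stands is that full-sample screening is an inference.

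**Inflation is not unconditional.** A reader might infer that the AUC is inflated whatever the threshold, even when no marker is informative. The figures do not support that: at the only levels the protocol names there is no null inflation, and at 5% Bonferroni it is about 0.01. The severe values belong to levels that the protocol permits but does not name.

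**The example pair is not simply wrong.** It is introduced as something that may be done, it still controls type I error because it is stricter than 5% Bonferroni, and stage 1 contemplates interactions that would raise the number of tests. The false discovery rate rule in 3.F.3 belongs to a screen described as hypothesis-generating. What stands is that the example and the two rules are not reconciled.

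**No shortfall against Table 7 follows.** A reader might infer that the strict example makes the accuracies in Table 7 unattainable. The documents do not support a numerical comparison. The threshold is illustrative, and the simple formula does not reproduce the table: for 5 markers and 10 auxiliary predictors at effect 0.2, Φ(√(5×0.04 + 10×0.01)) = 0.708, against a tabulated PCC* of 0.788. Retention at effect 0.4 is also undetermined: 47% or 0.2%, depending on how the distance between classes is defined, which 3.F.5.b does not say.

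**Some detail may belong in a SAP.** Ridge tuning and the reporting format may. The order of screening and splitting is a procedure that the protocol itself sets out.

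**Conclusion.** The concern holds in conditional form. On the natural sequential reading of 3.F.4, the averaged AUC is optimistic and choosing alpha by it favours the most over-fitted screen. Null inflation is negligible at 10^-8, small at 5% Bonferroni and severe from about 10^-4 upwards. With modest real signal, bias is already visible at 5% Bonferroni (0.66 against 0.59). The leak is the main fault; reuse of the AUC for selection is minor.

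The strict example does not remove the problem. The protocol plans several alpha levels without fixing them and leaves the false discovery rate open. At its own effect size of 0.2 almost no true marker passes 10^-8, so looser levels, where the leak is large, are likely to be tried.

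The sizes rest on independent normal markers and the assumed ridge penalty and prevalence. A short run at 30% prevalence (10 replicates) gave the same pattern: 0.500, 0.500, 0.727, 0.947 and 1.000. The direction follows from the order of the steps.

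**What to change.** In 3.F.4, state that in each of the 100 rounds all response-based work is done on the training part only: stage 1 correlations and choice of terms, univariate screening, choice of α_m and α_c, and ridge tuning, with inner cross-validation for the choices. Report the mean outer-loop AUC and its spread over rounds as the performance of the whole procedure. Then apply the procedure once to all data to obtain the final model. If re-screening inside each round was always intended, one sentence saying so settles the first part.

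Secondary: align the example thresholds either with the Bonferroni rule they cite (2.5×10^-6 and 6.8×10^-4 for a 5% level over 20,000 and 74 tests) or with the false discovery rate rule of 3.F.3, and say which screen feeds the prediction model.

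The cost is wording and computing time. The reported AUC will be lower but honest. It may also be somewhat conservative for the final model, because each round trains on only 135 or 170 participants: in the signal example above, 0.66 inside the rounds at 10^-3 against 0.78 in new patients for the model fitted to all 200.

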For example, if we have 50 molecular markers and 10 auxiliary variables, from the sample size of 200, we will be able to reach a 99.6% PCC* with the average effect size of a single molecular marker to be 0.4, and the relative effect size of the auxiliary predictor to the molecular marker to be 0.5. This 99.6% PCC* almost reaches the optimum PCC of 99.9%, yet it is very realistic because the sample size of 200 falls in our recruitment targets.

It is noted that the inclusion of patients without the specified diseases of interest will not affect the power of classifier designed for this study as long as the required sample sizes given

in Table 7 are met. Such additional information from the third cohort might be useful in the development of a different classifier in an auxiliary study where the clinical status of these patients is of interest.

3.F.5.c. Sample Size and Power Related to the MN Cohort Study

Under the same assumption given in the power calculation for the FSGS/MCD cohort study, we can also calculate the power of the MN cohort study in the same fashion. And the result provided in Table 7 above (3.N-1) can also be applied to the MN cohort study.

For example, if we have 100 molecular markers and 10 auxiliary variables, from under the sample size of 150, the PCC* is 76.6% with δ_m/σ_m being 0.2 and the relative effect size of the auxiliary being 0.5. If we increase the sample size from 150 to 200, we can find an increase of PCC* from 76.6% to 83.7%.

3.F.5.d. Sample Size and Power Related to the cNEPTUNE Study

The analytic plan for this cohort is to identify groups of participants by clinical relapse and remission patterns as well as functional, molecular and genetic profiles, with a goal to relate those groups to clinically meaningful outcomes, including patient reported outcomes. As these subgroups are yet to be defined by the data obtained by the cohort, we present a range of exposures and minimum detectable odds ratios below. In the pediatric population, and as seen in the current NEPTUNE cohort, rates of clinically significant decline in kidney function, defined as a 40% drop in eGFR or ESRD, ranged from 0.00 to 0.16 per person-year, and as such, the study is not primarily powered to this event.

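### Section 3.F.5.b calls the assumptions behind Table 7 conservative, but the table treats the molecular markers as mutually independent while section 3.F.3 expects them to be highly correlated

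*Protocol*

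**What the plan says.** Section 3.F.5.b takes the probability of correct classification (PCC) as the measure of predictive power. PCC* is the accuracy of the optimal linear classifier built on the true predictors, and PCC(n) is what a given sample size achieves. The section describes the basis of the table as "The results given in Table 6 are based on a simplified analysis with conservative assumptions". The reference to Table 6 is a numbering slip, since the PCC results stand in Table 7.

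The stated inputs are a single average effect size per marker, "the relative effect size of the auxiliary predictor to the molecular marker is 0.5", and "ρ is the correlation between molecular markers and auxiliary predictors, and $\rho=0$ is assumed in Table 7". Nothing is said about correlation among the markers themselves.

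The worked example for FSGS/MCD says that at n=200, "if we have 50 molecular markers and 10 auxiliary variables", "we will be able to reach a 99.6% PCC* with the average effect size of a single molecular marker to be 0.4". It calls this figure realistic because 200 lies within the recruitment targets. In Table 7 the 0.996 is the PCC(n=200) entry, and PCC* is 0.999. Section 3.F.5.c applies the same table to MN and quotes 83.7% at n=200 for 100 markers of effect 0.2.

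Section 3.F.3 describes the markers to be analysed: "For example, biomarkers in a common transcriptional network may form a molecular signature panel". It chooses its method for that structure: "Ridge regression enables us to bypass the analytic difficulty due to highly correlated biomarkers in the model and hence obtain robust results".

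**The concern.** The accuracy calculation and the analysis plan appear to describe different predictor structures. One adds up 50 or 100 separate signals. The other expects co-regulated genes that partly repeat one another. When markers in a panel all push in the same direction and are positively correlated, each further marker adds less than its own squared effect. Assuming independence then overstates the attainable accuracy. Ridge regression stabilises the fit in such data, but no linear classifier can exceed the optimal one.

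What is at stake is a stated performance property of the study. A reader who takes the assumptions as conservative will treat 99.6% and 83.7% as figures the study should at least match.

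**Working it through.** **Inputs.** From section 3.F.5.b and Table 7: r_m markers (5, 50 or 100), r_c = 10 auxiliary predictors, effect e = δ_m/σ_m (0.2 or 0.4), relative auxiliary effect k = 0.5, correlation zero between the two sets. Not in the protocol, and assumed here: panel size s and within-panel correlation ρ.

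**Step 1: reproduce the printed ceilings under full independence.** PCC* = Φ(√(r_m·e² + r_c·(k·e)²)).

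| r_m | e | printed PCC* | k = 0.5 (stated) | k = 1.0 |
|---|---|---|---|---|
| 5 | 0.2 | 0.788 | 0.708 | 0.781 |
| 5 | 0.4 | 0.941 | 0.863 | 0.939 |
| 50 | 0.2 | 0.941 | 0.926 | 0.939 |
| 50 | 0.4 | 0.999 | 0.998 | 0.999 |
| 100 | 0.2 | 0.982 | 0.979 | 0.982 |
| 100 | 0.4 | 0.99999 | 0.99997 | 0.99999 |

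With k = 1.0 all six cells agree within 0.007. With the stated 0.5, the two r_m = 5 cells miss by about 0.08.

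**Step 2: check that the markers themselves are treated as independent, whatever k was used.** Invert each printed ceiling to (z/e)², the number of full-strength independent signals it implies. At e = 0.2 this gives 15.98, 61.09 and 109.93 for r_m = 5, 50 and 100. Going from 5 to 50 markers adds 45.1 for 45 extra markers, and going from 50 to 100 adds 48.8 for 50. At e = 0.4 the first step adds 59.68 − 15.27 = 44.4 for 45. Each marker therefore adds about its full squared effect, which is what mutual independence gives. The auxiliary term cancels in these differences.

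**Step 3: ceilings with correlated panels.** For equal, same-direction effects with exchangeable correlation ρ in panels of size s, the marker term becomes r_m·e² / (1 + (s − 1)·ρ).

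For r_m = 50, e = 0.4, s = 10, the independent marker term is 50 × 0.16 = 8. The auxiliary term is 10 × 0.04 = 0.4 (k = 0.5) or 10 × 0.16 = 1.6 (k = 1.0).

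| ρ | marker term | ceiling, k = 0.5 | ceiling, k = 1.0 |
|---|---|---|---|
| 0 | 8 | 0.998 | 0.999 |
| 0.1 | 8/1.9 = 4.21 | 0.984 | 0.992 |
| 0.3 | 8/3.7 = 2.16 | 0.945 | 0.974 |
| 0.5 | 8/5.5 = 1.45 | 0.913 | 0.960 |

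These are infinite-sample optima, so no sample size can exceed them under these assumptions. The protocol's figure at n=200 is 0.996.

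For the MN example (r_m = 100, e = 0.2, printed ceiling 0.982), the same panels give 0.931/0.861/0.819 with k = 0.5 and 0.943/0.888/0.856 with k = 1.0. Only the 0.819 lies below the quoted 83.7%.

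**Step 4: where the ceiling crosses 0.996.** Φ⁻¹(0.996)² = 7.033. The ceiling falls below 0.996 when (s − 1)·ρ exceeds 8/(7.033 − 0.4) − 1 = 0.206 (k = 0.5), or 8/(7.033 − 1.6) − 1 = 0.472 (k = 1.0). In panels of 10 that is ρ above about 0.02 or 0.05. In panels of 5 it is about 0.05 or 0.12.

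**Step 5: sensitivity to direction.** Keep r_m = 50, e = 0.4, panels of 10 and ρ = 0.1/0.3/0.5, and reverse the effect of some markers in each panel.
- One of ten reversed: 0.997/0.996/0.998 with k = 1.0, and 0.994/0.992/0.996 with k = 0.5.
- Two of ten reversed: 0.999/0.999/1.000 with k = 1.0, and 0.997/0.998/1.000 with k = 0.5.

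**The case against.** The strongest reply is that the loss depends on assumptions the protocol never makes. It gives no within-panel correlation, no panel size and no effect signs. Step 5 shows that a few reversed markers per panel can bring the ceiling back to 0.996 or above. Panels of 5 with correlation 0.1 give 0.9966 with k = 1.0. This stands. A reader might infer that 99.6% exceeds the theoretical maximum, or cannot hold under the protocol's own description of the data. The documents do not support that, because section 3.F.3 says the biomarkers are correlated but not how strongly, or in which direction they act.

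It can also be said that the sample size does not rest on 99.6%. Table 7 has an r_m = 5 block with PCC(n=200) of 0.687 and 0.896. The synopsis in section 1.B quotes 75%-96% for FSGS/MCD at 250 and 70%-94% for MN at 200. This stands too: nothing here shows that 200 or 250 participants are too few.

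Finally, the section openly calls the analysis simplified, states one zero correlation, and does not say which assumptions are the conservative ones. That softens the criticism but does not remove it. Independence among markers is not disclosed. It is a favourable choice in the natural reading of a single average effect shared by co-regulated genes, and no argument is offered for the label.

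**Conclusion.** The label conservative is not supported. Table 7 rests on mutually independent markers, whereas the plan expects to analyse highly correlated ones. That the markers are treated as independent is inferred from the printed ceilings and not written in the protocol, but the agreement in steps 1 and 2 is close.

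The size can only be illustrated. With same-direction effects, panels of 10 and correlation 0.1 to 0.5, the ceiling behind the 99.6% example falls to between 0.984 and 0.913 at the stated auxiliary effect, or between 0.992 and 0.960 at the value that reproduces the table. With mixed directions, or with small and weakly correlated panels, there may be no loss below 99.6%. No finite-sample loss is claimed.

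A second discrepancy came out of the check: the stated relative auxiliary effect of 0.5 does not reproduce the r_m = 5 ceilings (0.708 and 0.863 against 0.788 and 0.941).

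**What to change.** In section 3.F.5.b:

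- Delete the word conservative and correct the table reference.
- State that Table 7 assumes molecular markers independent of each other as well as of the auxiliary predictors.
- State which relative auxiliary effect was actually used, and correct either the text or the table.
- Add sensitivity rows over a range of within-panel correlations, for example 0.1, 0.3 and 0.5, or values seen in expression profiles the network already holds. Give the panel size and the assumption on effect direction.
- Present 99.6%, and 83.7% in section 3.F.5.c, as independence-case figures, and drop the description of the first as realistic. Label both as PCC at the given n, not as PCC*.

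The cost is a re-run of the existing calculation with a block correlation and an edited table. Some quoted accuracies may become less favourable. Enrolment, endpoints and data collection do not change.
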